## 8.3.3. Hypoglycemia

The following classifications of hypoglycemia are used to characterize hypoglycemic events:

#### Level 1 hypoglycemia:

Glucose <70 mg/dL (3.9 mmol/L) and  $\geq$ 54 mg/dL (3.0 mmol/L): Level 1 hypoglycemia can alert a person to take action such as treatment with fast-acting carbohydrates. Providers should continue to counsel participants to treat hypoglycemia at this glucose alert value.

#### Level 2 hypoglycemia:

Glucose <54 mg/dL (3.0 mmol/L): Level 2 hypoglycemia is also referred to as documented or blood glucose confirmed hypoglycemia with glucose <54 mg/dL (3.0 mmol/L). This glucose threshold is clinically relevant regardless of the presence or absence of symptoms of hypoglycemia.

#### Level 3 hypoglycemia:

Severe hypoglycemia: A severe event characterized by altered mental and/or physical status requiring assistance for treatment of hypoglycemia. For example, a participant with altered mental status, and could not assist in their own care, or was semiconscious or unconscious, or experienced coma with or without seizures, and the assistance of another person was needed to actively administer carbohydrate, glucagon, or other resuscitative actions. Glucose measurements may not be available during such an event, but neurological recovery attributable to the restoration of glucose concentration to normal is considered sufficient evidence that the event was induced by a low glucose concentration.

The determination of a hypoglycemic event as an episode of severe hypoglycemia, as defined above, is made by the investigator based on the medical need of the participant to have required assistance and is not predicated on the report of a participant simply having received assistance. If a hypoglycemic event meets the criteria of severe hypoglycemia, the investigator must record the event as serious on the AE CRF and report it to Lilly as an SAE. In addition, the investigator will be asked to determine whether the episode was preceded by repeated or prolonged episodes of hypoglycemia.

Nocturnal hypoglycemia is a hypoglycemia event (including severe hypoglycemia) that occurs at night and presumably during sleep (between midnight and 6 AM).

## 8.3.4. Systemic Hypersensitivity Reactions

Many drugs, including oral agents and biologic agents, carry the risk of systemic hypersensitivity reactions. If such a reaction occurs, additional data should be provided to the sponsor in the designated CRFs.

Sites should have appropriately trained medical staff and appropriate medical equipment available when study participants are receiving study intervention. It is recommended that participants who experience a systemic hypersensitivity reaction be treated per national and international guidelines.

In the case of generalized urticaria or anaphylaxis, additional blood and urine samples should be collected as described in Section 10.2, Appendix 2, "Laboratory Assessments for Hypersensitivity Events". Laboratory results are provided to the sponsor via the central laboratory.

#### 8.3.5. Injection site reactions

Symptoms and signs of a local injection/infusion site reaction may include erythema, induration, pain, pruritus, and edema.

If an ISR (Injection-Site Reaction) is reported by a participant or site staff, the ISR CRF will be used to capture additional information about this reaction (for example, injection-site pain, degree and area of erythema, induration, pruritis and edema). If an injection-site event is reported, the AE will be recorded, and additional data will be provided to the sponsor in the eCRF.

#### 8.3.6. Adjudicated events: Cerebrocardiovascular Events

Potential cerebrocardiovascular events will be identified by the investigative site or by a medical review conducted by the sponsor or designee.

A blinded external Clinical Event Committee will adjudicate the events in a consistent and unbiased manner. Events include

- death
- myocardial infarction
- stroke or Transient Ischemic Attack (TIA)
- hospitalization for unstable angina
- hospitalization for heart failure, and
- coronary revascularization procedure.

## 8.4. Pharmacokinetics

At the visits and times specified in the SoA (Section 1.3), blood samples will be collected for all participants. Only samples from participants assigned to treatment with LY3209590 will be analyzed for drug concentration. Instructions for the collection and handling of blood samples will be provided by the sponsor. The actual date and time (24-hour clock time) of each sampling will be recorded.

## Bioanalytical

Samples will be analyzed at a laboratory designated by the sponsor and stored at a facility designated by the sponsor. Concentrations of LY3209590 will be assayed using a validated bioanalytical method.

# 8.5. Pharmacodynamics

Pharmacodynamic parameters will be evaluated as described in Sections 3 and 9.3.6.1.

# 8.6. Genetics

Genetics are not evaluated in this study.

# 8.7. Biomarkers

Biomarker research is performed to address questions of relevance to drug disposition, target engagement, PD, mechanism of action, variability of study participant response (including safety), and clinical outcome. Sample collection is incorporated into clinical studies to enable examination of these questions through measurement of biomolecules including DNA, RNA, proteins, lipids, and other cellular elements.

Serum and plasma samples for non-pharmacogenetic biomarker research will be collected at the times specified in the Schedule of Activities (Section 1.3) where local regulations allow.

Samples will be used for research on the drug target, disease process, variable response to LY3209590 pathways associated with T2D, mechanisms of action of LY3209590 and/or research methods, or in validating diagnostic tools or assay(s) related to T2D.

# 8.8. Immunogenicity Assessments

At the visits and times specified in the SoA (Section 1.3), venous blood samples from all study participants will be collected for analysis to determine antibody production against LY3209590. Antibodies may be further characterized for cross-reactive binding to endogenous insulin.

To interpret the results of immunogenicity, a corresponding venous blood sample will be collected at the same visits to determine the concentrations of LY3209590 (PK sample). At Visit 3, the sample for immunogenicity should be taken predose; however, the PK sample for LY3209590 will be taken postdose.

Instructions for the collection and handling of blood samples will be provided by the sponsor.

Treatment-emergent ADAs are defined in Section 9.3.6.2. Immunogenicity will be assessed by a validated assay designed to detect and characterize ADA in the presence of LY3209590 at a laboratory approved by the sponsor.

Sample retention is described in Section 10.1.12.

## 8.9. Health Economics

Health economics or medical resource utilization and health economics parameters are not evaluated in this study

# 9. Statistical Considerations

The first version of the SAP will be finalized prior to first participant visit and it will include a more technical and detailed description of the statistical analyses described in this section. This section is a summary of the planned statistical analyses of the most important endpoints, including primary and key secondary endpoints.

# 9.1. Statistical Hypotheses

## **Primary Hypothesis**

The primary objective of this study is to test the hypothesis that LY3209590 is noninferior to insulin degludec on glycemic control as measured by change from baseline to Week 26 (Visit 22) in HbA1c in participants with T2D currently on basal insulin. The null hypothesis ( $H_0$ ) to be tested is the difference in the change from baseline to Week 26 (Visit 22) in HbA1c (LY3209590 – insulin degludec) is greater than the noninferiority margin (NIM). The NIMs of 0.4% and 0.3% will both be tested to meet different regulatory requirements. The 2-side 95% confidence interval (CI) will be used for testing the noninferiority.

## **Secondary Hypotheses**

The key secondary (multiplicity adjusted) objectives are to test the hypotheses that LY3209590 is superior to insulin degludec with respect to

- change from baseline in HbA1c at Week 26 (Visit 22)
   *H*0: the difference (LY3209590 insulin degludec) ≥0.0
- the event rate of nocturnal hypoglycemia (<54 mg/dL [3.0 mmol/L] or severe) during treatment period up to Week 78 (Visit 37)

   H0: the relative event rate (LY3209590 vs. insulin degludec) ≥1
- time in glucose range between 70 and 180 mg/dL (3.9 and 10.0 mmol/L) inclusive measured by CGM collected during the CGM session prior to Week 26 (Visit 22)

*H*0: the difference (LY3209590 – insulin degludec)  $\leq 0.0$ 

These hypotheses and the primary hypothesis will be tested using a strategy to control the overall type 1 error (see Section 9.1.1.1).

## 9.1.1.1. Multiplicity Adjustment

A graphical approach (Bretz et al. 2009; 2011) for multiple comparisons will be used to ensure the strong control of overall type I error rate for testing the primary and key secondary (multiplicity adjusted) objectives. The overall significance level ( $\alpha$ ) will be set to 0.05. The total  $\alpha$  will be used for the primary objective first, then the  $\alpha$  will be allocated and transitioned to other key secondary objectives once the primary objective is met. The testing procedure and  $\alpha$ allocation will be established according to the clinical importance and statistical power of the endpoints in this study population. The details of graphical testing scheme will be described in the SAP.

# 9.2. Analyses Sets

Analysis Populations/Data Sets	Description
Entered Population	All participants who sign the informed consent form.
Randomized Population	All randomized participants. Participants will be analyzed according to the treatment they were assigned.
mITT Population	All randomized participants who took at least 1 dose of study treatment. Participants will be analyzed according to the treatment they were assigned.
EAS1	The data will include
	mITT population excluding participants discontinuing the study
	treatment due to inadvertent enrollment, and
	• all measurements regardless of the use of study treatment or the
	initiation of rescue medication.
EAS2	The data will include
	mITT population excluding participants discontinuing the study
	treatment due to inadvertent enrollment, and
	• measurements up to the discontinuation of study treatment or the
	initiation of rescue medication.
SS	The data will include
	• mITT population, and
	• all measurements regardless of the use of study treatment or the
	initiation of rescue medication.

The following populations are defined for purpose of analysis:

Abbreviations: EAS = efficacy analysis set; mITT = modified intent-to-treat; SS = safety analysis set.

# 9.3. Statistical Analyses

## 9.3.1. General Considerations

Statistical analysis of this study will be the responsibility of Lilly or its designees. Any change to the data analysis methods described in the protocol will require an amendment ONLY if it changes a principal feature of the protocol. Any other changes to the data analysis methods described in the protocol, and the justification for making the change, will be described in the SAP or the clinical study report. Additional exploratory analyses of data will be conducted as deemed appropriate.

Unless otherwise stated, the efficacy analyses will be conducted on either EAS1 (for treatment regimen estimand) or EAS2 (for efficacy estimand) and the safety analyses will be conducted on SS. All tests of treatment effects using statistical models will be conducted at a 2-sided alpha level of 0.05 and 2-sided 95% CI will be provided. Unless otherwise specified, other secondary and tertiary efficacy measures will be analyzed using EAS2 with the data up to the discontinuation of study treatment (defined by the date of last study dose + 10 days) or the initiation of rescue medication whichever is earlier.

## 9.3.2. Primary Endpoint/Estimand Analysis

The primary objective is to compare the HbA1c change from baseline to Week 26 between LY3209590 and insulin degludec and will be based on either of the 2 estimands: *treatment regimen estimand* for the US FDA submission and *efficacy estimand* for registrations in other countries.

The *treatment regimen estimand* will be estimated using the HbA1c data at baseline and Week 26 (Visit 22) for the EAS1, regardless of the use of study treatment or rescue medications. The missing measures at the primary endpoint will be imputed using multiple imputation by the retrieve dropout approach. The retrieved dropout participants are those who discontinue IP prior to Week 26 (Visit 22) but have non-missing measures at Week 26 (Visit 22). If there are only a limited number of retrieved participants that leads to a failure in performing the multiple imputation analysis, such as the model cannot converge, or the number of retrieved dropout participants is small, the missing HbA1c at Week 26 (Visit 22) will be imputed by return-to-baseline multiple imputations. After the imputation, the observed and imputed data will be analyzed by the analysis of covariance (ANCOVA). The model will include treatment, strata (country, and the type of basal insulin at randomization), and baseline value of the dependent variable. The statistical inference will be based on the multiple imputation framework by Rubin (1987).

The *efficacy estimand* is the treatment differences in the change in HbA1c from baseline to Week 26 (Visit 22) if all participants would adhere to the treatment without intercurrent events. The EAS2 with data up to the discontinuation of study treatment or the initiation of rescue medication, whichever is earlier, and the HbA1c collected at all planned postbaseline visits will be used in the analysis. There may be missing values due to the early discontinuation of study treatment or use of rescue medication. The mixed-model repeated measures (MMRM) model will be used, and the missing values will be handled in the MMRM analysis under the assumption of missing at random. The MMRM model will include treatment, strata (country, and the type of basal insulin at randomization), visit and treatment-by-visit interaction as fixed effects, and baseline of the dependent variable as a covariate. The Kenward-Roger approximation will be used to estimate denominator degrees of freedom for the MMRM models. An unstructured covariance structure will be used to model the within-participant errors. If this structure fails to converge, the following covariance structures will be used in order until one converges:

- 1. Toeplitz with heterogeneity
- 2. autoregressive with heterogeneity
- 3. compound symmetry with heterogeneous variances
- 4. Toeplitz
- 5. Autoregressive
- 6. compound symmetry without heterogeneous variances.

The 2-sided 95% CI of the least-squares (LS) mean for individual treatment groups, treatment LS mean difference (LY3209590 – insulin degludec) in the HbA1c change from baseline to Week 26 (Visit 22) will be estimated. For both estimands, LY3209590 will be declared noninferior to

insulin degludec if the upper limit of the 2-side 95% CI for the LS mean difference in the HbA1c change from baseline is below NIM (+0.4% or +0.3% for different regulatory requirements).

The HbA1c is reported in unit of % and will be converted to the unit of mmol/mol using the following formula:

HbA1c in mmol/mol = 10.93 \* HbA1c in % - 23.5 (http://www.ngsp.org/ifccngsp.asp).

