## 4.2. Scientific Rationale for Study Design

This study will evaluate the efficacy and safety of once-weekly basal insulin LY3209590 compared to once-daily insulin degludec in adult participants with T2D already treated with basal insulin. A 2:1 randomization ratio of LY3209590: insulin degludec will allocate more participants for safety and exposure information to the LY3209590 treatment group. The 78-week treatment period provides collection of more efficacy and safety information for the experimental treatment. Insulin doses will be titrated to the same FBG targets of 80–120 mg/dL (4.4–6.6 mmol/L) for both treatment groups.

This is an open-label study. Investigators, participants, and study-site personnel will be unblinded to the assigned treatment. To eliminate potential biases, designated members of the Lilly study team will remain blinded throughout the study (see Section 6.3). Only a minimum number of Lilly personnel will see the randomization table and treatment assignments before the study is complete.

The primary efficacy measurement is HbA1c, a widely used measure of glycemic control that reflects a cumulative history of glucose levels in the preceding 2 to 3 months. The primary endpoint at Visit 22 (Week 26) is based on participants reaching stable insulin dose by 8 to 12 weeks and achieve glycemic stability in advance of the 26-week primary endpoint. The secondary objectives provide complementary information about glycemic control. Hypoglycemia, AEs, and immunogenicity will be assessed to characterize safety.

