## **Insulin Dose Titration and Dose Maintenance**

In this treat-to-target study, both treatment groups will undergo titration to achieve and maintain an FBG target within the range of 80-120 mg/dL (4.4-6.6 mmol/L). Active titration will occur in both treatment groups between Visits 3 to 15 (Weeks 0 to 12) which will be designated as the Titration Period with the goal to achieve insulin dose stabilization by Visit 15 (Week 12) with a minimum of monthly adjustments as necessary during the Maintenance Period from Visit 15 to 37 (Weeks 12 to 78).

Using the e-diary-linked study-provided glucometer, participants in both treatment groups will perform daily self-monitored FBGs. A minimum of 3 FBG readings on separate days each week must be obtained so that investigators can review the data to make dose adjustments using the titration algorithms for once-weekly or once-daily insulins (Sections 6.1.4 and 6.1.5). The median FBG to use in determining the dose adjustments starting at Visit 5 (Week 2) is obtained from the 3 most recent FBGs in the previous week. The median is the middle value when the 3 values are placed in ascending or descending order. For example, if a participant's FBGs for the past 3 consecutive measurements were 180, 202, and 190, the median is 190.

**Note:** If the participant has only 2 FBG readings for the week, then the lesser of the readings should be used to determine the dose adjustments. If only 1 FBG measurement is available, determination if dose is changed using only a single FBG value is at the discretion of the investigator.

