# 9.5. Sample Size Determination

Approximately 939 participants will be randomly assigned to LY3209590 and insulin degludec in a 2:1 ratio. With the assumption of 15% dropout at Week 26, approximately 532 and 266 participants will complete 26 weeks of treatment on LY3209590 and insulin degludec, respectively.

The primary objective of this study is to test the hypothesis that LY3209590 is noninferior to insulin degludec on glycemic control as measured by change from baseline to Week 26 (Visit 22) in HbA1c in participants with T2D currently on basal insulin.

Assuming a noninferiority margin (NIM) of 0.4%, no true difference between treatment groups, and a SD of 1.1%, 798 completers (532 on LY3209590 and 266 on insulin degludec) will provide greater than 99% statistical power to show noninferiority between LY3209590 and insulin degludec using the upper limit of a 2-sided 95% confidence interval (LY3209590 – insulin degludec). This sample size also has at least 95% statistical power to show noninferiority between LY3209590 and insulin degludec using a 0.3% NIM at Week 26.

The 798 completers will provide 95% statistical power to demonstrate the superiority (LY3209590 vs. insulin degludec) of change in HbA1c from baseline to 26 weeks (assuming a SD of 1.1% and true mean difference is -0.3%) using the alpha of 0.05.

The 798 completers will provide at least 95% statistical power to show the superiority of the percentage of time in glucose range between 70 and 180 mg/dL (3.9 and 10.0 mmol/L) inclusive during the CGM session prior to Week 26 between LY3209590 and insulin degludec (assuming a SD of 18% and true mean difference is 5%) at alpha = 0.05.

The 798 participants will provide at least 80% statistical power to show the superiority of the event rate of clinically significant nocturnal hypoglycemia (<54 mg/dL [3.0 mmol/L] or severe) during treatment phase up to Week 78 (assuming event rate of 0.67 [SD = 2.6] and 1.1 [SD = 2.6] events per participant per year for LY3209590 and insulin degludec, respectively) using a negative binomial distribution at alpha = 0.05.

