4.3.2. Main Analytical Approach

The primary objective is to test the hypothesis that LY3209590 is noninferior to insulin degludec on glycemic control in the targeted study population. The noninferiority test will be based on: *treatment regimen estimand* for the US FDA submission and *efficacy estimand* for registrations in other countries. The full significance level of 0.05 will be used for each estimand.

	Treatment Regimen Estimand	Efficacy Estimand
Analysis	All participants in EAS1 with non-missing	All participants in EAS2 with non-missing
Population	baseline measure	baseline measure and at least one non-missing
		post-baseline scheduled measure
Analysis	All non-missing observations at baseline and	All non-missing observations at baseline and all
Data	Week 26 (Visit 22) regardless of the use of	scheduled post-baseline timepoints during
	study intervention or rescue medications.	treatment period (that is, Weeks 2, 4, 12, 16, 26,
		36, 52, 64 and 78) prior to the date of last study
		dose + 10 days for LY3209590 and +1 day for
		Insulin Degludec, or the initiation of rescue
		medication whichever is earlier (for participants
		with an intercurrent event).
Missing	There may be missing values at Week 26	There may be missing values due to the early
Data	(Visit 22) due to early study discontinuation.	discontinuation of study intervention or use of
	The missing values will be imputed using	rescue medication. The MMRM model will be
	multiple imputation by the retrieved dropout	used, and the missing values will be handled in
	approach. The retrieved dropout participants	the MMRM analysis under the assumption of
	are those who discontinue study intervention	missing at random.
	prior to Week 26 but have non-missing	
	measures at Week 26 in the same treatment	
	arm. If there are only a limited number of	
	retrieved participants (i.e., at least 1 arm has	
	less than 8 participants who discontinued	
	study treatment early and who have	
	endpoint visit measurements) or the model	
	cannot converge, the missing HbA1c at	

This table provides the details of treatment regimen estimand and efficacy estimand.

	Treatment Regimen Estimand	Efficacy Estimand
	Week 26 will be imputed by return-to-	
	baseline multiple imputation approach (Qu	
	and Dai 2022).	
Analysis	After the imputation, the observed and	The MMRM model will include treatment, strata
Model	imputed data will be analyzed by the	(country, and the type of basal insulin at

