	ANCOVA model using treatment, strata	randomization), visit and treatment-by-visit
	(country, and the type of basal insulin at	interaction as fixed effects, and baseline of the
	randomization), and baseline value of the	dependent variable as a covariate. The Kenward-
	dependent variable as independent variables.	Roger approximation will be used to estimate
	The statistical inference will be based on the	denominator degrees of freedom for the MMRM
	multiple imputation framework by Rubin	models. An unstructured covariance structure will
	(1987).	be used to model the within-participant errors. If
		this structure fails to converge, the following
		covariance structures will be used in order until
		one converges:
		1. Toeplitz with heterogeneity
		2. autoregressive with heterogeneity 3.
		compound symmetry with heterogeneous
		variances
		4. Toeplitz
		5. Autoregressive
		6. compound symmetry without heterogeneous
		variances.

Abbreviation: ANCOVA = analysis of covariance; EAS1 = Efficacy Analysis Set 1; EAS2 = Efficacy Analysis Set 2; HbA1c = hemoglobin A1c; MMRM = mixed model repeated measurement.

The 2-sided 95% CI of the LS mean difference (LY3209590 – insulin degludec) in the HbA1c change from baseline to Week 26 (Visit 22) will be estimated. For both estimands, LY3209590 will be declared noninferior to insulin degludec if the upper limit of the 2-side 95% CI for the LS mean difference in the HbA1c (measured in %) change from baseline is below NIM of +0.4%. In addition, the 95% CI for the LS mean difference will be compared to an alternative NIM of +0.3%.

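### The HbA1c MMRM uses one baseline slope for all nine visits, which can under-adjust Week 26; a baseline-by-visit term costs almost nothing and removes the risk.

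*Protocol*

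**What the plan says.** Protocol 9.3.2 gives the efficacy-estimand model as treatment, country, type of basal insulin, "visit and treatment-by-visit interaction as fixed effects, and baseline of the dependent variable as a covariate". SAP 4.3.2 repeats it ("interaction as fixed effects, and baseline of the" dependent variable as a covariate) and lists the visits: Weeks 2, 4, 12, 16, 26, 36, 52, 64 and 78. On the covariance, the protocol states: "An unstructured covariance structure will be used to model the within-participant errors". Six simpler structures follow if that one does not converge. Neither document includes a baseline-by-visit interaction or explains its absence.

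The same model carries the HbA1c superiority test (SAP 4.4.1.2) and the Week 52 and 78 analyses (SAP 4.4.2.1). The treatment regimen estimand uses a single-visit ANCOVA at Week 26, so its baseline slope is specific to that week.

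**The concern.** Protocol 4.2 says that HbA1c "reflects a cumulative history of glucose levels in the preceding 2 to 3 months", and Protocol 6.1.3 places active titration in Weeks 0 to 12. At Week 2, HbA1c can have moved little whatever the baseline. By Week 26 of a treat-to-target trial that admits 6.5% to 10%, participants who start higher should have fallen further. The slope of change on baseline should therefore steepen over visits, while the model holds it constant.

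With an unstructured covariance, the common slope is a precision-weighted combination of the visit slopes. If early visits have the smaller residual variance, which the same lag suggests, they dominate. Week 26 then gets a slope that is too shallow, and some of the variance that baseline could explain stays in the treatment contrast.

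Two features of this plan raise the stakes. Randomization is stratified by HbA1c (below 8.0%, or 8.0% and above), but the HbA1c models omit that stratum, so the baseline covariate is the only adjustment for it. SAP 2.1 also pairs the tighter 0.3% margin with this estimand.

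**Working it through.** **The plan's own figures.** Protocol 9.5 begins: "Assuming a noninferiority margin (NIM) of 0.4%, no true difference between treatment groups, and a SD of 1.1%, 798 completers". Completers are 0.85 × 626 = 532 and 0.85 × 313 = 266. SE = 1.1 × √(1/532 + 1/266) = 0.0826. Power is Φ(0.4/0.0826 − 1.96) = 99.8% and Φ(0.3/0.0826 − 1.96) = 95.3%. The superiority figure at −0.3% is also 95.3%. All three stated powers reproduce.

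**Formula.** Let β be the vector of true visit slopes of change on baseline, S the residual covariance given baseline, s the baseline SD and r the residual SD at Week 26. With complete data and an unstructured covariance, the fitted common slope is

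b = (1′S⁻¹β) / (1′S⁻¹1),

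and the Week 26 variance becomes r² + (β₂₆ − b)²s². The share of the Week 26 adjustment that is lost is L = ((β₂₆ − b)/β₂₆)². L above 1 means worse than no baseline adjustment. The documents give none of β, S or s, so every value below is assumed.

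**Two-visit illustration.** Take residual SD 0.25 at Week 2 and 0.85 at Week 26, with slopes −0.10 and −0.45.
- Correlation 0: the weights are proportional to 0.85² = 0.7225 (Week 2) and 0.25² = 0.0625 (Week 26). Then b = (−0.07225 − 0.028125)/0.785 = −0.128 and L = (0.322/0.45)² = 51%. Week 26 variance rises by 0.322²s²/0.7225, which is 9% at s = 0.8 and 14% at s = 1.0.
- Correlation 0.4: subtract 0.4 × 0.25 × 0.85 = 0.085 from each weight. This gives 0.6375 and −0.0225, b = −0.087 and L = 65%. The variance rises by 12% to 18%. The Week 26 weight turns negative once the correlation exceeds 0.25/0.85 = 0.29, so b can move past the Week 2 slope.
- Equal residual SDs: the weights are equal, b = −0.275 and L = 15%. With nine visits, most of them late, the loss is smaller still.

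**Nine visits.** Results over assumed slope paths, residual SD paths and correlations:

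| Setting | Share of Week 26 adjustment lost |
|---|---|
| Equal slopes at all visits | 0% |
| Constant residual SD | 1-11% |
| Mild drift (−0.25 to −0.45), rising residual SD | 13-44% |
| Larger drift (−0.10/−0.15 to −0.50/−0.60), rising residual SD | 31-141% |

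More than half is lost in 12 of the 36 unequal-slope scenarios. The SE ratio (planned model over baseline-by-visit) runs from 1.00 to 1.34, with median about 1.02.

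Examples of the variance arithmetic:
- Mild drift, mildly rising SD (r = 0.80, s = 0.85, b = −0.283 against −0.45): 0.167² × 0.85²/0.64 = 3%.
- Same slopes, constant SD (b = −0.393): 0.057² × 0.85²/0.64 = 0.4%.
- Residual SD rising from 0.25 to 0.85, weak slope change (b = −0.11 against −0.35, s = 0.8): (0.24 × 0.8/0.85)² = 5%.
- Same SDs, strong slope change (b = +0.03 against −0.55, s = 1.0): (0.58 × 1.0/0.85)² = 47%.

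The largest SE ratio, 1.34, is a 79% variance increase (1.339² = 1.79). It is a corner of the grid in which the common slope does clearly worse than no adjustment.

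**Simulation with missing data** (n = 939, about 15% MAR dropout by Week 26, 40 runs per scenario). Model-based SE ratios were 1.24 (steep), 1.06 (moderate) and 1.00 (flat). In the steep case the common slope was fitted at +0.105 against −0.603, so L = (0.708/0.603)² = 138%. Bias under the planned and extended models was 0.009 and 0.005, −0.013 and −0.011, and −0.013 and −0.013. These differences are at most 0.0035, against a Monte Carlo error of about 0.06/√40 = 0.01.

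**Power at the 0.3% margin.** The documents do not say whether the SD of 1.1% is before or after baseline adjustment.
- If unadjusted: with s = 0.85 and slope −0.5, the fully adjusted SD is √(1.21 − 0.181) = 1.015 and power is 97.6%. With half the adjustment lost, the SD is 1.058 and power 96.5%. With all of it lost, power is 95.3%.
- If already adjusted: losing 25-100% of the adjustment gives 94.9% down to 89.0%. The low end has s = 1.0 and slope −0.6: SD = √(1.21 + 0.36) = 1.253. Power at the 0.4% margin there is still 98.9%.

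**Cost of the term.** Nine slopes replace one, so there are 8 more parameters. On 798 participants, with about 20 fixed effects taken as given, the SE grows by √(778/770) = 1.005.

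**The case against.** The strongest reply is that a single baseline covariate is a valid, prespecified choice, that the size of the loss cannot be taken from the documents, and that the median SE increase over the assumed scenarios is about 2%. All of that stands. Four stronger readings are tempting and do not hold.

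- *Most of the adjustment is lost.* That needs both a steep change in slope and a marked rise in residual SD. Both are plausible for HbA1c, but neither can be shown from the documents, and two thirds of the unequal-slope scenarios lose less than half.
- *The Week 26 estimate is biased or the test invalid.* With complete data, randomization keeps the contrast unbiased, and the misfit is absorbed into the estimated covariance, so the SE is honest. With MAR dropout a misspecified mean could bias the estimate in principle, but the simulations, which are small, show no clear difference between the models.
- *Every MMRM endpoint suffers.* TRIM-D and EQ-5D-5L have no early scheduled post-baseline visit; apart from early termination they are collected at Weeks 26, 52 and 78. SMBG fasting glucose and insulin dose use compound symmetry (SAP 4.4.2.1), so no visit has a lower modelled variance. CGM sessions start at Week 4, and CGM and fasting glucose lack the HbA1c lag.
- *The stated power is not met.* If 1.1% is an unadjusted SD, the stated 95% at the 0.3% margin holds unless the common slope does worse than no adjustment. A shortfall otherwise requires that 1.1% is already baseline-adjusted, which the documents do not say.

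**Conclusion.** The point holds as one of precision in the HbA1c MMRM for the efficacy estimand. The common slope is a fact of the plan. That the true slope steepens between Week 2 and Week 26 follows reasonably from the HbA1c lag and the titration period. The consequence at Week 26 runs from negligible, with near-constant residual SD or mild drift, to about 20-45% more variance with steep drift and sharply rising residual SD. Larger figures appear only where the fitted common slope clearly has the wrong sign, and I would not rely on them. All of these sizes rest on assumed slopes, residual SDs, correlations and baseline SD. The US analysis is unaffected.

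The case for acting is the asymmetry: about 0.5% on the SE at worst, against a gain that may be nil or substantial.

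**What to change.** Add a baseline-by-visit interaction to the HbA1c MMRM in SAP 4.3.2, before database lock. This covers the Week 26 noninferiority and superiority tests and the Week 52 and 78 analyses. It also aligns the baseline adjustment with the Week 26-specific slope of the treatment regimen ANCOVA. If the sponsor keeps the common slope, the SAP should say why.

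Protocol 9.3.1 allows changes of method that are not principal features to be described and justified in the SAP, so the statements in SAP Sections 1 and 4.9 that nothing has changed would need an entry. The subgroup MMRMs in SAP 4.7.2.1 are fitted separately by subgroup with the same model, and the 0.5% figure does not apply to small categories, so the SAP should state whether the term carries over. For other MMRM endpoints the term is optional.

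Cost: eight fixed-effect parameters and a line of code; no new data, visits or participants.
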